3.6.1 Withdrawal of Consent

Subjects who request to discontinue study treatment will remain in the study and must continue to be followed for protocol specified follow-up procedures. The only exception to this is when a subject specifically withdraws consent for any further contact with him/her or persons previously authorized by subject to provide this information. Subjects should notify the investigator of the

decision to withdraw consent from future follow-up **in writing**, whenever possible. The withdrawal of consent should be explained in detail in the medical records by the investigator, as to whether the withdrawal is from further treatment with study drug only or also from study procedures and/or post treatment study follow-up, and entered on the appropriate CRF page. In the event that vital status (whether the subject is alive or dead) is being measured, publicly available information should be used to determine vital status only as appropriately directed in accordance with local law.

3.6.2 *Lost to Follow-Up*

All reasonable efforts must be made to locate subjects to determine and report their ongoing status. This includes follow-up with persons authorized by the subject as noted above. Lost to follow-up is defined by the inability to reach the subject after a minimum of three documented phone calls, faxes, or emails as well as lack of response by subject to one registered mail letter. All attempts should be documented in the subject's medical records. If it is determined that the subject has died, the site will use permissible local methods to obtain the date and cause of death.

If investigator's use of third-party representative to assist in the follow-up portion of the study has been included in the subject's informed consent, then the investigator may use a Sponsor-retained third-party representative to assist site staff with obtaining subject's contact information or other public vital status data necessary to complete the follow-up portion of the study. The site staff and representative will consult publicly available sources, such as public health registries and databases, in order to obtain updated contact information. If after all attempts, the subject remains lost to follow-up, then the last known alive date as determined by the investigator should be reported and documented in the subject's medical records.

4 TREATMENTS

Study drugs include both Non-investigational (NIMP) and Investigational Medicinal Products (IMP) and can consist of the following:

- All products, active or placebo, being tested or used as a comparator in a clinical trial.
- Study required premedication, and
- Other drugs administered as part of the study that are critical to claims of efficacy (eg, background therapy, rescue medications)
- Diagnostic agents: (such as glucose for glucose challenge) given as part of the protocol requirements must also be included in the dosing data collection.

4.1 Study Treatments

Nivolumab 100 mg (10 mg/mL) will be packaged in an open-label fashion. Ten BMS-936558 (nivolumab), 10 mL vials will be packaged within a carton (see [Table 4.1-1](#)), and are not subject or treatment arm specific. Vial assignments by subject will be made through the IVRS (interactive voice response system) to track usage and resupply.

As described in [Section 3.1](#), nivolumab will be dosed intravenously at 3 mg/kg every two weeks. After 1 year (52 weeks) of treatment the subjects who are still on the study and benefiting from the therapy will be randomized (1:1) via IVRS to one of the two cohorts, Cohort A or Cohort B.

Subjects randomized to Cohort A will be treated until disease progression, unacceptable toxicity, or withdrawal of informed consent. Subjects randomized to Cohort B will discontinue treatment at 1 year (52 weeks). Subjects in Cohort B will remain on the study and will follow all study assessments [REDACTED]. At progression, subjects in Cohort B may receive retreatment [REDACTED].

Subjects who are retreated can continue until progression, unacceptable toxicity, or withdrawal of informed consent. Study treatment can continue beyond initial investigator assessed progression, as specified in criteria presented in [Section 4.3.4 Treatment Beyond Disease Progression](#).

Table 4.1-1: Product Description

Product Description and Dosage Form	Potency	Primary Packaging (Volume)/ Label Type	Secondary Packaging (Qty) /Label Type	Appearance	Storage Conditions (per label)
BMS-936558-01 Solution for Injection	100 mg (10 mg/mL)	10 mL vial/ Open-label	10 vials per carton/ Open-label	Clear to opalescent, colorless to pale yellow liquid. May contain particles.	2 to 8° C. Protect from light, shaking, and freezing.

NOTE: Medications used to treat BMS-936558 (nivolumab)-related infusion reactions are (eg, diphenhydramine, acetaminophen/paracetamol, corticosteroids) considered NIMPs (noninvestigational products) and will not be provided by the sponsor. These will be obtained by the investigational sites as marketed product, which should be stored in accordance to the package insert. For further details related to these medications and BMS-936558 (nivolumab)-related infusion reactions, please see [Section 4.3.6](#).

4.1.1 *Investigational Product*

An investigational product, also known as investigational medicinal product in some regions, is defined a pharmaceutical form of an active substance or placebo being tested or used as a reference in a clinical study, including products already with a marketing authorization but used or assembled (formulated or packaged) differently than the authorized form, or used for an unauthorized indication, or when used to gain further information about the authorized form.

The investigational product should be stored in a secure area according to local regulations. It is the responsibility of the investigator to ensure that investigational product is only dispensed to study subjects. The investigational product must be dispensed only from official study sites by authorized personnel according to local regulations.

In this protocol, investigational product(s) is/are: BMS-936558 (nivolumab) Solution for Injection

4.1.2 *Non-investigational Product*

Other medications used as support or escape medication for preventative, diagnostic, or therapeutic reasons, as components of the standard of care for a given diagnosis, may be considered as non-investigational products.

In this protocol, non-investigational product(s) is/are: any medications used to treat BMS-936558 (nivolumab) related infusion reactions (see [Section 4.3.6](#)).

4.1.3 *Handling and Dispensing*

The product storage manager should ensure that the study drug is stored in accordance with the environmental conditions (temperature, light, and humidity) as determined by BMS. If concerns regarding the quality or appearance of the study drug arise, the study drug should not be dispensed and contact BMS immediately. BMS-936558 (nivolumab) vials must be stored in the refrigerator at 2-8°C, protected from light and freezing. If stored in a glass front refrigerator, vials should be stored in the carton.

Investigational product documentation must be maintained that includes all processes required to ensure drug is accurately administered. This includes documentation of drug storage, administration and, as applicable, storage temperatures, reconstitution, and use of required processes (eg, required diluents, administration sets).

For non-investigational product, if marketed product is utilized, it should be stored in accordance with the package insert, summary of product characteristics (SmPC), or similar.

Recommended safety measures for preparation and handling of BMS-936558 (nivolumab) include laboratory coats and gloves.

After BMS-936558 (nivolumab) has been prepared for administration, the total storage time (combination of refrigeration and room temperature) is not to exceed 24 hours. For details on prepared drug storage and use time under room temperature/light and refrigeration, please refer to the current BMS-936558 (nivolumab) Investigator Brochure.⁹

Care must be taken to assure sterility of the prepared solution as the product does not contain any anti-microbial preservative or bacteriostatic agent. No incompatibilities between BMS-936558 (nivolumab) and polyolefin bags have been observed.

BMS-936558 (nivolumab) was administered as a 60 minute IV infusion. As of Protocol Amendment 04, a 30 minute infusion will be used for all subjects; Subjects enrolled before Protocol Amendment 04 will be switched to the 30 minutes infusion. A volumetric pump with a 0.2/0.22 micron in-line filter at the protocol-specified doses will be used. Nivolumab is not to be administered as an IV push or bolus injection. At the end of the infusion, flush the line with a sufficient quantity of normal saline (per institutional standard of care).

Details regarding the mixing and concentrations of the dose (preparation) will be found in the current Investigator brochure for BMS-936558 (nivolumab).⁹

4.2 Method of Assigning Subject Identification

After the subject's eligibility is established and informed consent has been obtained, the subject will be enrolled and a number will be assigned through an interactive voice response system (IVRS). Also, the IVRS will be used to manage staggered enrollment of subject subgroups, and to randomize subjects at 1 year (52 weeks, \pm 2 weeks) as well as to track the randomized subjects from subgroups to cohorts. Specific instructions and procedures for using IVRS will be provided to the investigational site in a separate document/ manual.

The investigator (or designee) will register the subject for enrollment by following the enrollment procedures established by BMS. The following information is required for enrollment:

- Date of informed consent
- Date of birth
- Gender at birth
- Diagnosis (ie, SQ or NSQ NSCLC)
- Number of lines of therapy with confirmed progression
- PS

The subjects who complete 1 year (52 weeks) of study treatment and are still benefiting from the nivolumab treatment will be randomized (1:1) via IVRS to one of the two cohorts, Cohort A or Cohort B.

4.3 Selection and Timing of Dose for Each Subject

Subjects will receive treatment with nivolumab as a 30 minute IV infusion, on Day 1 of a treatment cycle every 2 weeks. Dosing calculations should be based on the body weight assessed as per [Table 5.1-2](#). The dose should remain the same if the subject's weight is within 10% of the baseline weight. All doses should be rounded to the nearest milligram. There will be no dose escalations or reductions of nivolumab allowed. Subjects may be dosed no less than 12 days from the previous dose. There are no premedications recommended for nivolumab on the first

cycle. If an acute infusion reaction is noted, subjects should be managed according to [Section 4.3.6](#).

Subjects will be monitored continuously for AEs while on study. Treatment modifications (eg, dose delay or discontinuation) will be based on specific laboratory and adverse event criteria.

Early recognition and management may mitigate severe toxicity. Evaluation and Management Guidelines were developed to assist investigators and can be found in the Investigator Brochure:

- Suspected Pulmonary Toxicity
- Diarrhea and Colitis
- Suspected Hepatotoxicity (including asymptomatic liver function tests [LFT] elevations)
- Suspected Endocrinopathy
- Nephrotoxicity

For subjects expected to require more than 4 weeks of corticosteroids or other immunosuppressants to manage the adverse event, consider recommendations provided in Sections 4.3.1 to Section 4.3.3.

4.3.1 Dose Delay Criteria

Tumor assessments for all subjects should continue as per protocol even if dosing is delayed.

4.3.1.1 Nivolumab Dose Delay Criteria

Nivolumab administration should be delayed for the following:

- Grade 2 non-skin, drug-related AE, with the exception of fatigue
- Grade 2 drug-related creatinine, AST, ALT and/or total bilirubin abnormalities
- Grade 3 skin, drug-related AE
- Grade 3 drug-related laboratory abnormality, with the following exceptions:
 - Grade 3 lymphopenia or asymptomatic amylase or lipase does not require dose delay
 - Grade ≥ 3 AST, ALT, total bilirubin will require dose discontinuation
- Any adverse event, laboratory abnormality, or intercurrent illness which, in the judgment of the investigator, warrants delaying the dose of study medication.

Subjects who require delay of nivolumab should be re-evaluated weekly or more frequently if clinically indicated and resume nivolumab dosing when re-treatment criteria are met.

4.3.2 Dose Reductions

There will be no dose modifications of nivolumab.

4.3.3 Criteria to Resume Treatment with Nivolumab

- Subjects may resume treatment with nivolumab when the drug-related AE(s) resolve(s) to Grade ≤ 1 or baseline, with the following exceptions: Subjects may resume treatment in the presence of Grade 2 fatigue.
- Subjects who have not experienced a Grade 3 drug-related skin AE may resume treatment in the presence of Grade 2 skin toxicity.

- Subjects with baseline AST/ALT or total bilirubin in the Grade 1 toxicity range who require dose delays for reasons other than a 2-grade shift in AST/ALT or total bilirubin may resume treatment in the presence of Grade 2 AST/ALT OR total bilirubin
- For subjects with Grade 2 AST, ALT and/or total bilirubin Abnormalities, dosing may resume when laboratory values return to baseline and management with corticosteroids, if needed, is complete.
- Subjects with combined Grade 2 AST/ALT AND total bilirubin values meeting discontinuation parameters should have treatment permanently discontinued
- Drug-related pulmonary toxicity, diarrhea, or colitis must have resolved to baseline before treatment is resumed. Drug-related endocrinopathies adequately controlled with only physiologic hormone replacement may resume treatment
- If treatment is delayed > 6 weeks, the subject must be permanently discontinued from study therapy, except as specified in [Section 4.3.5](#).
- Subjects in Cohort B will also be allowed to resume treatment upon progression

Subjects with drug-related endocrinopathies adequately controlled with only physiologic hormone replacement may resume treatment after consultation with the BMS Medical Monitor (or designee). Adrenal insufficiency requires discontinuation regardless of control with hormone replacement.

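### For a subject with Grade 1 baseline liver tests and a drug-related rise to Grade 2 in the same test, Sections 4.3.1.1 and 4.3.3 give conflicting hold and resume instructions, and nothing says which prevails.

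*Combined protocol and SAP*

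**What the plan says.** Three provisions bear on a subject who enters with a mildly raised liver test.

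- **Delay (Section 4.3.1.1).** Dosing is delayed for "Grade 2 drug-related creatinine, AST, ALT and/or total bilirubin abnormalities". The trigger is an absolute grade; baseline is not mentioned. At the next level the section states "Grade ≥ 3 AST, ALT, total bilirubin will require dose discontinuation". A delayed subject is to "resume nivolumab dosing when re-treatment criteria are met", which points to Section 4.3.3.
- **Resume, Grade 1 baseline bullet (Section 4.3.3).** It opens "Subjects with baseline AST/ALT or total bilirubin in the Grade 1 toxicity range who require dose delays for" and continues "reasons other than a 2-grade shift in AST/ALT or total bilirubin may resume treatment in the presence of Grade 2 AST/ALT OR total bilirubin".
- **Resume, Grade 2 liver bullet (Section 4.3.3, immediately after).** "For subjects with Grade 2 AST, ALT and/or total bilirubin Abnormalities, dosing may resume when laboratory values return to baseline", and any corticosteroid management must also be complete. It carries no restriction on baseline grade.

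The general rule that opens Section 4.3.3 is "Subjects may resume treatment with nivolumab when the drug-related AE(s) resolve(s) to Grade ≤ 1 or baseline", followed by exceptions.

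Such subjects can be enrolled. Section 3.3.1 admits AST and ALT up to, but not including, three times the upper limit of normal, and the Grade 1 baseline bullet presupposes that they exist.

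**The concern.** The two hepatic bullets of Section 4.3.3 overlap for one kind of subject and give that subject different answers, while Section 4.3.1.1 treats the value as a reason to withhold drug. Table 5.1-2 has liver function reviewed before each infusion, so the conflict arises at the dosing decision itself. One site could re-dose at Grade 2 and another could wait for baseline. Each could cite the protocol, and neither action would show up as a deviation.

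The first thing at stake is subject safety, because the rule decides whether drug is given again during an unresolved liver signal. The second is consistency of exposure across sites. Hepatitis is one of the select adverse event categories, so handling at Grade 2 could influence whether an event becomes high grade. The documents give no means of sizing that influence.

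**Working it through.** No sample size, power or error-rate figure is involved. The check sets the rules side by side for each combination of baseline grade and current grade.

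| Baseline and current value | 4.3.1.1 | Grade 1 baseline bullet, 4.3.3 | Grade 2 liver bullet, 4.3.3 | Conflict? |
|---|---|---|---|---|
| Grade 1 ALT; ALT now Grade 2, drug-related | Delay | May resume at Grade 2 (1-grade shift) | Resume on return to baseline | Yes, all three |
| Grade 1 ALT; delayed for another event; ALT now Grade 2, drug-related | Delay | May resume at Grade 2 | Resume on return to baseline | Yes, all three |
| Grade 1 ALT; ALT now Grade 2, not drug-related | Liver item not triggered | May resume at Grade 2, if delayed for another reason | Resume on return to baseline | Between the two bullets only |
| All liver tests normal; one now Grade 2, drug-related | Delay | Does not apply | Resume on return to baseline | No |
| Grade 1 ALT, normal bilirubin; bilirubin now Grade 2, drug-related | Delay | Excluded by the proviso (2-grade shift) | Resume on return to baseline | No |
| Grade 1 ALT; ALT now Grade 3, drug-related | Discontinue; the 4.3.5 footnote and the Appendix 2 hepatic algorithm leave room for continuation or delay | If delayed, excluded by the proviso | Not addressed at Grade 3 | Not this point |

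The first row is the core case:

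1. Grade 2 minus Grade 1 is a 1-grade shift, so the delay is for something other than a 2-grade shift and the permissive bullet applies.
2. The next bullet also applies, because the value is Grade 2 and the bullet does not depend on baseline.
3. If the subject resumes under the permissive bullet, the value is still drug-related Grade 2 and again meets the delay criterion of 4.3.1.1.

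**Rough size.** Inputs are the hepatic row of Table 1.1-1 at 3 mg/kg (3 of 54 any grade, 2 of 54 Grade 3-4) and the planned 1280 treated subjects.

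- Below Grade 3: 3 − 2 = 1 of 54, or 1.9%.
- Projected: 1280 × 1/54 = 23.7, about 24.
- Share with a Grade 1 baseline: not in the documents; assumed 10-30%.
- Affected: 0.10 × 23.7 = 2.4 to 0.30 × 23.7 = 7.1, roughly 2-7 subjects.

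As a sensitivity check across all doses, 18 − 4 = 14 of 306 were below Grade 3. Then 1280 × 14/306 = 58.6, and 10-30% of that is 5.9 to 17.6, roughly 6-18 subjects.

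**The case against.** The strongest reply is that Section 4.3.3 reads as a general rule with listed exceptions. On that view the Grade 1 baseline bullet is a specific exception and the Grade 2 liver bullet covers everyone else. The wording is also permissive: it obliges nobody to re-dose, and Section 4.3.1.1 provides weekly re-evaluation and investigator judgment. This reading is reasonable and could settle Section 4.3.3 internally. The text does not state it, however, and it leaves Section 4.3.1.1 untouched: the subject resumed at Grade 2 still meets an unqualified delay criterion.

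A reader might infer more than the documents support, in three ways:

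- **That the 2-grade-shift proviso is empty,** so that every Grade 2 hepatic delay in a subject with a Grade 1 baseline qualifies for immediate resumption. It is not empty. It excludes a rise from normal to Grade 2 in bilirubin when only ALT was Grade 1 at baseline, and it can apply to a Grade 3 case that is delayed under the Section 4.3.5 footnote or the hepatic algorithm. It simply does not resolve the same-test, 1-grade case.
- **That all hepatic events count,** giving 1280 × 3/54 = 71 subjects before the baseline share is applied. Two of those three events were Grade 3-4 and fall outside this point.
- **That the secondary outcome measures are directly affected.** Section 8.3.2 limits time to resolution to Grade 3-4, and Section 8.4.3 describes immune-modulating treatment in subjects with high-grade select events. An event that stays at Grade 2 enters neither, nor the primary endpoint. It would appear only in the exploratory safety summaries of Section 8.4.4.1.

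**Conclusion.** The inconsistency is real but narrow. It concerns a subject with Grade 1 baseline AST/ALT or total bilirubin whose same test rises to drug-related Grade 2. For that subject one provision delays, one permits resumption at the current value, and one ties resumption to return to baseline. No order of precedence is given. If the Grade 2 value is not drug-related, only the two Section 4.3.3 bullets differ.

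The count of roughly 2-7 subjects is indicative only. It rests on a single event among 54 subjects with mixed tumor types, that event may have been Grade 1, and the 10-30% share is an assumption. The case rests on the conflicting text, not on the count. The consequence is for subject safety and uniform dosing; any effect on the high-grade endpoints is indirect and cannot be quantified from the documents. It is worth correcting because it is a safety instruction and the correction is cheap.

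**What to change.** The sponsor must reconcile Section 4.3.1.1 with the two hepatic bullets of Section 4.3.3, so that a subject with a Grade 1 baseline and a Grade 2 on-study value in the same liver test falls under one delay rule and one resume rule. The revised text should state which of the two bullets governs when the Grade 2 value is drug-related. Which rule is clinically right is for the sponsor to decide, and none is proposed here.

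The cost is a wording change at the next amendment and a letter to sites. Data collection does not change.

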4.3.4 Treatment Beyond Disease Progression

As described in [Section 1.4.3.3](#), accumulating evidence indicates a minority of subjects treated with immunotherapy may derive clinical benefit despite initial evidence of PD. Subjects treated with nivolumab will be permitted to continue treatment beyond initial RECIST 1.1 defined progressive disease (PD) as long as the following criteria are met:

- 1) Investigator-assessed clinical benefit and do not have rapid disease progression
- 2) Tolerance of study drug
- 3) Stable performance status
- 4) Treatment beyond progression will not delay an imminent intervention to prevent serious complications of disease progression (eg, CNS metastases)
- 5) Subject provides written informed consent prior to receiving additional nivolumab treatment, using an ICF describing any reasonably foreseeable risks or discomforts, or other alternative treatment options.

The decision to continue treatment beyond initial progression should be discussed with the BMS medical Monitor and documented in the study records.

A radiographic assessment/ scan should be performed within 8 weeks of original PD to determine whether there has been a decrease in the tumor size, or continued PD. The assessment of clinical benefit should be balanced by clinical judgment as to whether the subject is clinically deteriorating and unlikely to receive any benefit from continued treatment with nivolumab.

If the investigator feels that the nivolumab subject continues to achieve clinical benefit by continuing treatment, the subject should remain on the trial and continue to receive monitoring according to the Time and Events Schedule on [Table 5.1-2](#).

For the subjects who continue nivolumab study therapy beyond progression, further progression is defined as an additional 10% increase in tumor burden volume from time of initial PD. This includes an increase in the sum of all target lesions and/ or the development of new measurable lesions. Treatment should be discontinued permanently upon documentation of further disease progression

New lesions are considered measurable at the time of initial progression if the longest diameter is at least 10 mm (except for pathological lymph nodes which must have a short axis of at least 15 mm). Any new lesion considered non-measurable at the time of initial progression may become measurable and therefore included in the tumor burden volume if the longest diameter increases to at least 10 mm (except for pathological lymph nodes which must have a short axis of at least 15 mm).

Subjects with global deterioration of health status who require discontinuation of treatment without objective evidence of disease progression at the time of treatment discontinuation should be reported as 'symptomatic deterioration'. Every effort should be made to document objective progression (ie radiographic confirmation) even after discontinuation of treatment.

